1 OBJECTIVES

1.1 Purpose, Specific Aims, or Objectives

In this project, we will assess whether messaging about ventilation from cigarette filters lowers cigarette product appeal among smokers. This study, part of a series (I 50217, I 59617) will help determine whether a regulatory requirement to reduce ventilation will lower demand for cigarettes without unintended consequences. This project will assess the effect of variation in pack messaging about filter ventilation on consumers' rating of product appeal, perceptions of health risks, and changes in cigarette consumption in a 2-week field study. Our *premise* is that messaging about risks of filter ventilation will reduce the appeal of cigarette smoking and increase the likelihood that smokers would either quit smoking or switch to an alternative product (e.g., electronic cigarettes). This project is well-integrated with the other studies in this P01, using the same standardized research cigarettes with defined ventilation characteristics and design parameters, as well as relying on common biobehavioral measures.

The aim of the proposed study is to assess how adding messaging to cigarette packages about filter vents and filters influences respondents' awareness of filter ventilation, beliefs about the function of filter vents and filters, smoking behavior, ratings of cigarette satisfaction, smoking topography, exposure to nicotine and carbon monoxide, perceptions about the risk of smoking, and intention to stop smoking.⁶ The protocol will consist of a randomized experiment via two-week field study.

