5 STUDY TIMELINES

5.1 Duration of an Individual Subject's Participation in the Study

The proposed study consists of multiple videoconferencing sessions (a total of 3) throughout a 2-week field study. Following informed consent, participants will be randomly assigned to 1 of 4 message conditions and use the assigned product for 2 weeks. This 2-week field study involves participants logging their use of tobacco products, while the weekly videoconferencing sessions involve additional questionnaires and guidance about field data collection.

Roswell Park Protocol Number: I 757820

	Data Collection Sessions (Weekly)			Field (Daily for 14 days)
	Video 1	Video 2	Video 3	Ecological Momentary Assessment
Tobacco Use Behavior				
Cigarettes per Day	X	X	X	X
Other Tobacco Use	X	X	X	X
Context of Use (e.g., location)				X
Questionnaires				
Message Perceptions (response, health risk, purchase)	X All messages	X Randomly Assigned Message	X Randomly Assigned Message	
Vent Awareness	X	X	X	
Product Evaluation (Duke Sensory, Product Evaluation Scale, Drug Effects, Hedonic Attribute)	X	X	X	X Select Items
Readiness to Quit (Contemplation Ladder)	X	X	X	
Withdrawal (MNWS, QSU-B, PANAS)				X Select Items
Attention to Messaging				X
Biomarkers				
Exhaled CO				X
Topography via Filter Analysis				X

Estimated date for the investigators to complete this study

Data collection should be completed by 12/31/2022.

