Remote Data Collection. Participants will complete the two-week study remotely using EMA methods. At the conclusion of Session 1, participants will be trained to record their assigned product use via EMA for data collection. Specifically, participants will respond to 5 scheduled questionnaires daily. These questionnaires are designed to assess product consumption, context of use (e.g., location, social situation), and subjective responses (e.g., withdrawal, product evaluation, message attention - more details on surveys provided below). Participants will be prompted to measure their exhaled-air CO level and product weight twice each day using a personal monitor provided to them. Participants will also retain all spent cigarette butts and unused products throughout the two weeks.

Day 3 Check-in: Research assistants will monitor EMA data to ensure the participant is compliant with study procedures. Participants will send a secure text message (via Twilio) or arrange a phone call to discuss the participant's compliance in the initial days of data collection. Participants that are not responding to prompts will be retrained to ensure they understand procedures and warned that compliance must increase to continue participating in the study.

Session 2 will take place one week later (\pm 2 days) via remote videoconference using an institution-approved software with a password protected meeting (e.g., WebEx, Microsoft Teams, Zoom). The Session 2 videoconference will include the completion of questionnaires on vent awareness, product evaluation, and readiness to quit (similar to Visit 1). Participants will again be asked on message perceptions, but only in relation to their randomly assigned condition.

Session 3 will take place one week later (\pm 2 days) via remote videoconference. The same questionnaires from Session 2 will be administered again. Laboratory staff will guide participants to place all materials (retained filter butts, unused products, unsigned payment receipts) in the provided shipping box. Arrangements will be made for the participant to return materials or for research staff to pick up materials. Participants will be paid for Visit 3 upon verification of returned study materials.

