11.4 Data To Be Collected

- **Baseline measures and covariates will assess:**
 - Demographics (age, sex, race/ethnicity, education, income)

Roswell Park Protocol Number: I 757820

- Tobacco use behaviors (consumption, brand, menthol preference, past quit attempts)
- Delay discounting
- A series of previously used items will assess knowledge and perceptions of filter vents.^{113,117}
- Nicotine dependence will be assessed using:
 - Fagerström Test for Nicotine Dependence (FTND¹¹⁸)
 - PROMIS

Behavioral aspects of cigarette dependence will be assessed using:

- The Glover-Nilsson scale^{120,121}
- The different scales are used to capture different dimensions of tobacco dependence.¹²²
- Exhaled air CO will be collected by the participants twice each day using a personal CO monitor provided by the researchers. The CO monitors provided are coVita iCo™ Smokerlyzers®, which are intended for research and consumer use and are compatible with a Smartphone or tablet (iOS or Android).

Perceptions of product messaging: In this study, we are interested in risk perceptions, smoking-related expectancies, and behavioral intentions. We will assess risk perceptions for specific products using a risk ladder.¹²⁹ More generalized perceptions of risk for cancer are captured using the tripartite risk (TRIRISK) measure, which captures deliberative, affective, and experiential components of risk perception.¹³⁰ The adult smoking consequences questionnaire (SCQ) will assess smoking-related expectancies.^{103,131} Behavioral intention is assessed using Juster's consumer purchase probability scale, a widely used marketing metric.¹³²⁻¹³⁴ Additional questions will include responses to messaging (e.g., message was powerful, memorable).

Responses to product use will be assessed in a number of ways: Response to nicotine dose will be assessed using the Minnesota Nicotine Withdrawal Scale (symptoms of nicotine withdrawal).¹³⁵ Cigarette craving in field will be assessed using the Brief QSU commonly used in cue reactivity research. Behavioral economic measures will assess product demand. A delay discounting task will assess preference for immediate reward,¹⁴⁸ while purchase tasks will be used to estimate level and elasticity of demand.¹⁴⁹⁻¹⁵¹ Sensory measures will be collected using the Duke Sensory Scale and Hedonic Attribute Scale. Drug effect measures include the Product Evaluation Scale and Drug Effects/Liking Scale.

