22 STATISTICAL PLAN

22.1 Data Analysis Plan

The analysis of EMA data will be analyzed using a linear mixed model with fixed effects for vent message (product design, color/name), as well as sex and other tobacco product strata (cigarettes only or dual use). The effect of packaging will be tested using a Bonferroni-corrected type-I error rate of 0.008 (0.05/6) to account for all possible pairwise comparisons of packaging types. Data from the field-study (e.g., change in product responses, risk, TNE, aldehyde-DNA adducts) will be analyzed using linear regression with terms in the model for vent message (no message, neutral, compensation, blocking), sex, and other tobacco product use.. Categorical outcomes for the field-study will be analyzed using logistic regression. As exploratory approaches, we will use time-varying effects models (TVEMs) to explore the effect of message condition on smoking behavior (product compliance), craving, risk perception, and quit intention in the EMA data.[191, 192] TVEMs have been used previously to examine treatment effects on craving [193] and relapse.[194] TVEMs will provide daily effect sizes, thereby allowing us to examine whether treatment effects (and relationships with other predictors) change over time (i.e., early vs. later in product switching). Responses at Visit 1 can be treated as time invariant predictors and mCEQ from EMA can be treated as time-varying predictor (and/or outcome) of product use.

Roswell Park Protocol Number: I 757820

We will enroll a total sample size of 300 subjects and assume a 20% drop-out rate with uniform drop-out from Visit 1 to Visit 3. This will result in a sample size of 300 subjects for Visit 1, 270 subjects for the first week of the field study, and 240 subjects for the end of field study. Our sample size was determined to have adequate power for the field study, For the field study, we hypothesize a 25% difference between conditions, corresponding to a 3.9 CPD difference. Assuming a standard deviation of 7.6,[195] a sample size of 240 subjects will provide 95% power to detect a significant difference between ventilation conditions at the 0.05 level and 80% power to detect a significant difference between packaging conditions with a Bonferroni-corrected type-I error rate of 0.008.

mCEQ is scored using an established algorithm.⁹⁶ This results in 3 subscales (Psychological Reward, Relief, Reward) and 2 single items (Aversion, Respiratory sensation). Scores range from 1-7.

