11. How worried are you about developing cancer in the future?
12. How fearful are you about developing cancer in the future?
13. How nervous are you about developing cancer in your lifetime?
14. When you think about cancer for a moment, to what extent do you feel fearful?
15. When you think about cancer for a moment, to what extent do you feel worried?
16. When you think about cancer for a moment, to what extent do you feel anxious?
17. How concerned are you about developing cancer in your lifetime?
18. How easy is it for you to imagine yourself developing cancer in the future?

Roswell Park Protocol Number: I 757820

PERCEIVED HEALTH RISK RATING: BASELINE

Based on using your usual brand cigarettes indicate what you believe your risk is for developing the following health problems on this scale from 1 to 10.

1. Lung Cancer _____
2. Emphysema _____
3. Bronchitis _____
4. Other Cancers _____
5. Heart Disease _____
6. Risk of Addiction _____
7. Stroke _____
8. Mouth Cancer _____
9. Tooth Loss _____

Minute Discounting 1000 92dd

Which would you rather have?
\$500 now \$1000 in 3 weeks

Which would you rather have?
\$500 now \$1000 in 1 day

Which would you rather have?
\$500 now \$1000 in 2 years

Which would you rather have?
\$500 now \$1000 in 4 hours

Which would you rather have?
\$500 now \$1000 in 4 days

Which would you rather have?

Roswell Park Protocol Number: I 757820

\$500 now \$1000 in 4 months

Which would you rather have?
\$500 now \$1000 in 8 years

Which would you rather have?
\$500 now \$1000 in 2 hours

Which would you rather have?
\$500 now \$1000 in 9 hours

Which would you rather have?
\$500 now \$1000 in 2 days

Which would you rather have?
\$500 now \$1000 in 1.5 weeks

Which would you rather have?
\$500 now \$1000 in 2 months

Which would you rather have?
\$500 now \$1000 in 8 months

Which would you rather have?
\$500 now \$1000 in 4 years

Which would you rather have?
\$500 now \$1000 in 18 years

Which would you rather have?
\$500 now \$1000 in 1 hour

Which would you rather have?
\$500 now \$1000 in 3 hours

Which would you rather have?
\$500 now \$1000 in 6 hours

Which would you rather have?
\$500 now \$1000 in 12 hours

Which would you rather have?
\$500 now \$1000 in 1.5 days

Which would you rather have?
\$500 now \$1000 in 3 days

Roswell Park Protocol Number: I 757820

Which would you rather have?
\$500 now \$1000 in 1 week

Which would you rather have?
\$500 now \$1000 in 2 weeks

Which would you rather have?

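### Two of the four outcomes planned for daily time-varying models, risk perception and quit intention, are not measured in the EMA, and the general risk scales have no documented follow-up

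*Combined protocol and SAP*

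**What the plan says.** Section 22.1 (Data Analysis Plan) introduces TVEMs as an exploratory analysis, to "explore the effect of message condition on smoking behavior (product compliance), craving, risk perception, and quit intention in the EMA data". It describes the output: "TVEMs will provide daily effect sizes, thereby allowing us to examine whether treatment effects (and relationships with other predictors) change over time". Separately, it plans a session-level analysis: "Data from the field-study (e.g., change in product responses, risk, TNE, aldehyde-DNA adducts) will be analyzed using linear regression".

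Risk perception matters to the study's purpose. Section 1.1 names "perceptions of health risks, and changes in cigarette consumption in a 2-week field study" among the effects to be assessed, and its aim paragraph lists both perceived smoking risk and intention to stop. Section 1.2 hypothesises an increase in intention to stop.

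On timing, the schedule in Section 5.1 marks the row beginning "Readiness to Quit (Contemplation Ladder" at Videos 1, 2 and 3 and not in the EMA column. The row for message perceptions, which includes a health-risk component, has the same pattern. Section 11.3 places TRIRISK in the Session 1 intake. For Session 2 it lists "questionnaires on vent awareness, product evaluation, and readiness to quit (similar to Visit 1"), plus message perceptions for the assigned condition; Session 3 repeats the Session 2 set. Section 11.4 explains TRIRISK's role: "More generalized perceptions of risk for cancer are captured using the tripartite risk (TRIRISK) measure". It also says that product-specific risk is rated on a risk ladder. Appendix C contains that ladder and a nine-item form headed "PERCEIVED HEALTH RISK RATING: BASELINE", which asks about the participant's usual brand.

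**The concern.** A TVEM estimates an effect as a smooth function of time and needs repeated measurements spread over the follow-up. If an outcome is never asked in the EMA, there is no daily series to which the model can be fitted. Three video sessions, two of them after exposure, cannot stand in for 14 days.

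The second issue is follow-up of general risk perception. If the scales that measure it are given only before participants use the labelled packs, the trial can describe who was enrolled but not whether a label changed that perception. The planned regression on change in risk would then depend on whichever other risk measure is repeated, and the plan does not name it.

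**Working it through.** No sample-size or power figure enters this point. The check is a cross-reference of each outcome named in Section 22.1 against the places where measurement is defined.

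**1. EMA occasions.** Sections 11.3 and 11.4 give 5 questionnaires a day for 14 days: 5 × 14 = 70 prompts. Appendix C describes 3 daily reports plus 2 to 3 pseudo-random prompts, which gives between 5 × 14 = 70 and 6 × 14 = 84. The choice does not affect the result, because the count for the two missing outcomes is zero either way.

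**2. EMA content.** The item list in Appendix C covers cigarette and other tobacco counts, product weight, craving and mood scales, selected hedonic and product-evaluation items, CO, label noticing and avoidance, context of the last cigarette, and four Duke sensory items. Sections 11.3 and 11.4 describe the same domains. The item nearest to quit intention asks whether the label led the participant to forgo a cigarette. That is a behaviour, not an intention to quit. No item asks about perceived health risk.

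**3. Measures against occasions.**

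| Measure | EMA prompts | Video sessions | After exposure |
|---|---|---|---|
| Smoking behaviour, including research versus other cigarettes | daily | cigarettes per day at 3 of 3 | yes |
| Craving | daily | not needed here | yes |
| Quit intention (contemplation ladder) | 0 of 70 | 3 of 3 | 3 − 1 = 2 sessions |
| Health risk within message perceptions | 0 of 70 | 3 of 3 | 3 − 1 = 2 sessions |
| TRIRISK (18 items) | 0 of 70 | 1 of 3, as listed | none documented |
| Perceived Health Risk Rating (9 items) | 0 of 70 | 1 of 3, by its title | none documented |

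So 2 of the 4 TVEM outcomes have data and 2 do not.

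**4. What the repeated health-risk element can support.** At Session 1 it is asked for all messages; at Sessions 2 and 3 only for the assigned condition. The documents do not say which form supplies it, nor what a participant with an unaltered pack rates. If it is the Health Risk Ladder in Appendix C, which asks where the cigarettes themselves belong, every arm can answer and change in product-level risk can be estimated. If it is a rating of the message, the no-message arm has nothing to rate at follow-up.

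**5. Smoking-specific risk.** The smoking consequences questionnaire, which includes items on smoking and health, is also listed only in the Session 1 intake.

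**The case against.** The strongest reply is that little depends on the faulty sentence. The TVEMs are labelled exploratory. Readiness to quit belongs to the first primary endpoint (Section 3) and is collected at all three videos, so the hypothesis about intention to stop remains testable. Health risk is also scheduled three times, and Section 22.1 has a separate regression for change in risk. With sessions about a week apart, a coarse week-1 versus week-2 comparison is possible. All of this stands.

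A reader might infer that risk perception and quit intention are absent from the dataset, or that the trial cannot address perceived health risk at all. The documents do not support that: both are missing daily, not missing altogether. Nor do they support the claim that the repeated risk rating concerns only the message. The Health Risk Ladder rates the cigarettes, and parts of the message battery ask about harm from the participant's own smoking.

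Two further replies stand in part. The nine-item form is known to be baseline-only from its title and usual-brand wording, and no session list schedules it by name; a follow-up version is not ruled out. TRIRISK measures personal cancer risk rather than the risk of smoking, is not a listed endpoint, and could serve as a baseline predictor, a use Section 22.1 allows for Visit 1 responses. Against that, Section 11.4 describes TRIRISK among the perception outcomes rather than in its list of baseline measures and covariates, and the smoking-specific items in the consequences questionnaire have no listed follow-up either.

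**Conclusion.** The point holds in a limited form. The exploratory daily models of risk perception and quit intention cannot be run as written: 0 of 70 EMA prompts measure either, so 2 of 4 named outcomes drop out. No primary analysis is affected, and session-level change can be estimated for readiness and for the message- or product-linked health-risk rating. TRIRISK and the Perceived Health Risk Rating have no documented administration after exposure, so the aim on perceived smoking risk rests on a repeated measure that the plan does not identify.

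This assumes that the Appendix C item list is complete, that the Session 2 and 3 lists in Section 11.3 are exhaustive, and that the nine-item form's title describes its use. The EMA conclusion is firm, because the schedule, the procedures and the item list agree. The conclusion on the nine-item form is the least certain.

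**What to change.** 1. In Section 22.1, limit the TVEMs to outcomes the EMA measures: smoking behaviour and craving.
2. Analyse readiness to quit and health risk in a repeated-measures model across Sessions 1 to 3. Take Sessions 2 and 3 as outcomes and the Session 1 value as covariate, with a condition-by-session term for the week-1 versus week-2 contrast.
3. Name the existing Health Risk Ladder as the repeated risk measure, so that all four arms, including no-message, can answer it. State which cigarettes it refers to at Session 1, where the product ratings concern the usual brand.
4. Repeat TRIRISK and the Perceived Health Risk Rating, the latter reworded to the study cigarettes, once at Session 3 in all arms. Adjust for the Session 1 value. Because of the rewording, the rating should be analysed with that value as a covariate rather than as a simple change score.

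Changes 1 and 2 are text only. Change 3 uses a form already in Appendix C. Change 4 adds 18 + 9 = 27 items to a visit that already consists of questionnaires, a few minutes by my estimate. It must be in place before participants finish, since a missed follow-up cannot be recovered.

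Adding daily risk and quit items to the evening prompt would rescue the original sentence, but I would not do it. Asking on 14 evenings may itself change the answers and may interact with a health-risk label differently from an unlabelled pack. It could also shift readiness and cigarettes smoked, both of which are primary endpoints.

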11.3 Study Procedures

The proposed study is a between-subjects design in which participants will be randomized to 1 of 4 conditions for 2 weeks.

- No Message (e.g., unaltered cigarette pack).
- Neutral Message: “Nothing about this product’s color or name means that it will protect a smoker from the health risks of smoking.”
- Compensation Message: “This product has a ventilated filter. Filter vents increase how deeply a smoker inhales without them knowing, which can increase the health risks of smoking.”
- Blocking Message: “This product has a ventilated filter. Be sure not to block the vent holes with your fingers or lips, which can increase the health risks of smoking.

Data will be collected in three remote video sessions and via EMA conducted over 2 weeks. Each study session is expected to take 0.5 hours. For each condition, active data collection is expected to take no more than 15 minutes. Study materials (cigarettes, CO monitor, containers for cigarette filter collection, scales) will be mailed to, delivered, or picked up by participants. Session 1 will involve confirmation of receipt of study materials, questionnaires, and training on procedures. Then, participants will track their product use via EMA app (REDCap) for 2 weeks, with two remote sessions via videoconference for additional questionnaires.

Informed Consent. An initial videoconferencing session will be used for informed consent. Consent will be obtained through the REDCap (Research Electronic Data Capture) system used for data collection. REDCap is a secure web-based application that supports data capture and management for research studies. The Investigator and Research Associate will design the study specific consent and upload the most recent CRS versions to the REDCap system. A secure link will be sent to each participant prior to the start time of the study. Research staff will guide the participant form, provide time to read the consent, and answer any questions. Participants and staff will be able to electronically sign, data, and submit the consent in real-time. Once the consent is submitted, it is automatically saved on RPCI protected servers. Access to this folder is restricted to authorized users. Standard protocols for data encryption (via Credant) when using laptops and USB drives will be followed.

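### The stated 80% power at the corrected level of 0.008 is about 55% for any one pair of message arms, and the 95% figure is for a ventilation contrast the trial does not have

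*Combined protocol and SAP*

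**What the plan says.** The sample size paragraph of Section 22.1 (combined protocol and SAP) sets enrolment and attrition: "We will enroll a total sample size of 300 subjects and assume a 20% drop-out rate", which leaves 240 at the end of the field study. The effect is given as "we hypothesize a 25% difference between conditions, corresponding to a 3.9 CPD difference".

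Two power figures follow from these inputs. The first, which uses an alpha of 0.05, reads "Assuming a standard deviation of 7.6,[195] a sample size of 240 subjects will provide 95% power to detect a significant difference between ventilation conditions". The second is "80% power to detect a significant difference between packaging conditions with a Bonferroni-corrected type-I error rate of 0.008". Earlier in Section 22.1 the corrected level is explained as a "Bonferroni-corrected type-I error rate of 0.008 (0.05/6) to account for all possible pairwise comparisons of packaging types".

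Section 11.3 describes a between-subjects design in which "participants will be randomized to 1 of 4 conditions for 2 weeks". The four conditions are no message, neutral, compensation and blocking. Section 11.2 supplies ventilated cigarettes to everyone. The listed Marlboro varieties are 30.6% or 37.6% ventilated, and which one a participant receives depends on whether they usually smoke menthol. The alternative laboratory-made cigarettes are also ventilated and are made to match. The models in Section 22.1 have terms for message, sex and other tobacco use, and none for ventilation level.

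**The concern.** Dividing the error rate by six only makes sense if the tests are the six pairwise comparisons among four arms. Each of those uses about half of the 240 completers, not all of them. A standardised difference near 0.5 with 60 per group is the familiar case for roughly 80% power at 0.05, so 80% at 0.008 looked too high. The 95% figure also names a comparison that this trial does not make.

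Cigarette consumption is the second primary endpoint in Section 3, and Section 11.4 calls the total number smoked the key outcome of the field study. Sections 1.2 and 11.1 predict no change in smoking behaviour, so a non-significant CPD result would tend to be read as confirming the hypothesis. How much weight such a null can bear depends on the power, and a reader who believes 80% would give it too much.

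**Working it through.** **Inputs from the documents**

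- Difference 3.9 CPD, SD 7.6, 240 completers, alpha 0.008 (0.05/6 = 0.00833): Section 22.1.
- Four between-subjects arms: Section 11.3.
- Implied reference mean: 3.9 / 0.25 = 15.6 CPD.

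**Assumptions, because the plan does not state them**

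- Equal allocation: 240 / 4 = 60 completers per arm.
- Two-sided tests, with no variance reduction beyond the stated SD.

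**Method.** Two-sample noncentral t. The noncentrality is δ / (σ√(2/n)), and power is the probability that t exceeds its critical value.

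- Standardised difference: 3.9 / 7.6 = 0.513.
- Standard error of a pairwise difference: 7.6 × √(2/60) = 1.388.
- Noncentrality: 3.9 / 1.388 = 2.81.

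**Trying to reproduce the 80%**

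| Comparison | Alpha | Power |
|---|---|---|
| 60 v 60, 118 df | 0.008 | 54.6% |
| 60 v 60, 118 df | 0.05/6 | 55.2% |
| 60 v 60, pooled error, 236 df | 0.008 to 0.05/6 | 55.5–56.0% |
| 60 v 60, normal approximation | 0.008 to 0.05/6 | 56.3–56.8% |
| 60 v 60, one-sided | 0.008 to 0.05/6 | 64–66% |
| 75 v 75 (all 300 retained) | 0.008 to 0.05/6 | 67–68% |
| 60 v 60 | 0.05, uncorrected | 79.6% |

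None of the corrected-level rows comes near 80%. Rounding 0.00833 to 0.008 moves the power by only about half a point. The uncorrected row does match 80%.

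**Trying to reproduce the 95%**

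- Two groups of 120 at 0.05 give 97.7%.
- If ventilation conditions loosely means message arms, 60 v 60 at 0.05 gives 79.6%.
- 95% at 0.05 needs about 99 per group.

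**What 60 per arm can detect, and what 80% would need**

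- Detectable difference with 80% power at 60 per arm: 4.92 CPD at 0.008 and 4.90 at 0.05/6. As a share of the mean, 4.9 / 15.6 = 31%.
- Completers per arm for 80% power at 3.9 CPD: 94 at 0.05/6 and 95 at 0.008 (92–93 by the normal approximation).
- Effective SD at which 60 per arm reaches 80%: about 6.0. With baseline adjustment, SD × √(1 − ρ²) = 6.0 requires a baseline correlation of about 0.61.
- If 7.6 were a single-day SD and the outcome a 14-day mean, its SD is 7.6 × √((1 + 13 × ICC)/14). Power at 0.05/6 is then 80%, 73%, 67% and 61% for intraclass correlations of 0.6, 0.7, 0.8 and 0.9.

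**The case against.** The strongest reply is that an unadjusted t-test is not the planned analysis. The diary data go into a linear mixed model over up to 14 days, and baseline CPD is collected. An effective SD of about 5.9–6.0 would give roughly 94–95% at 0.05 and 80–82% at 0.008 with 60 per arm, so both printed figures could come from a single calculation with the correction applied. That is a fair caution against saying how the 80% arose. The agreement with an uncorrected 0.05 is an observation, and nothing below depends on it. But the plan states 7.6, gives no baseline correlation, intraclass correlation or reduced SD, and lists no baseline CPD covariate in either model.

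A second reply is that a difference between packaging conditions might mean at least one significant result among the six. If exactly one arm differs from the other three by 3.9 CPD, that probability is 79.6–80.1%. The plan does not state that pattern, and the answer depends on it: about 61% if two arms lie halfway, and 87–88% if two arms differ from two. One arm against the other three pooled (60 v 180) gives about 78–79% at the corrected level, but it is not a pairwise comparison. What stands is that the plan must say which power it means.

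A third reply is that, with no behaviour change predicted, precision matters more than superiority power. That is reasonable, and it does not help the claim. The half-width of the corrected interval for one pair is 2.698 × 1.388 = 3.7 CPD, nearly the whole 3.9 CPD difference.

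**Conclusion.** The concern holds. On the printed inputs, with equal allocation and a two-sided unadjusted test, power for any one pairwise 3.9 CPD difference at the corrected level is about 55%, some 25 points below the figure stated. A true 25% difference between two given message arms would be missed about 45% of the time. Every route back to 80% needs an assumption that the plan does not make: an effective SD near 6.0, a baseline correlation of about 0.6, or any-pair power with one particular pattern of means.

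Separately, the 95% figure belongs to a contrast this trial does not randomise or model. It cannot be rescued by reading it as message arms.

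**What to change.** In Section 22.1, replace the power sentence with wording such as:

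> With equal allocation, 60 completers per message arm give about 55% power (two-sided, unadjusted) for any one pairwise difference of 3.9 CPD at alpha 0.008, and about 80% at an uncorrected 0.05. The difference detectable with 80% power at 0.008 is about 4.9 CPD (31%).

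Then:

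- State the allocation ratio, the sidedness, and whether the power is for one specified pair or for at least one pair. If it is for at least one pair, give the assumed pattern of means.
- Delete the power statement for ventilation conditions.
- If a baseline-adjusted or repeated-measures analysis is adopted for CPD, restate the power with the assumed baseline correlation or intraclass correlation shown, and say what kind of SD 7.6 is.
- Because no behaviour change is predicted, it would help to add the expected confidence interval width for a pairwise difference.

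The cost is wording in one section. The stated power becomes less favourable, but no participants, visits or data are added. Restoring 80% by sample size alone would take 94–95 completers per arm, which this fix does not require.
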